7.4.3 Sponsor Reporting Requirements to FDA

Once the DCC has been notified of a SAE/SSAR the following are the DCC's reporting requirements to the FDA:

Type of SAE/SSAR	Report to	Timeframe
Fatal or life-threatening, unexpected, and associated with study product/procedure	FDA	MedWatch submitted within 7 calendar days of learning of event
Other SAE/SSARs that are non-fatal or life-threatening but are unexpected and associated with study product/procedure	FDA	MedWatch submitted within 15 calendar days of learning of event

7.5 Unanticipated Problems (UPs)

An UP is an incident, experience, or outcome that specifically causes increased risk to the study or to its participants which may be of medical or non-medical etiology, and meets the following criteria:

- Unexpected (in terms of nature, severity, or frequency), given (a) the research procedures that are described in the protocol-related documents, such as the IRB-approved research protocol and informed consent document; and (b) the characteristics of the subject population being studied;
- Definitely, probably, or possibly related to participation in the research (i.e., there is a reasonable possibility that the incident, experience, or outcome may have been caused by the procedures or materials involved in the research); and
- Suggests that the research places subjects or others at a greater risk of harm (including physical, psychological, economic, or social harm) than was previously known or recognized.

All UP reporting will follow the same guidelines as noted above for SAE/SSAR reporting, and must include a corrective action plan/measures to prevent recurrence.

7.6 NHLBI DSMB Criteria

All SAEs and SSARs will be evaluated by the NHLBI DSMB in accordance with its charter and review procedures. This includes an assessment of expectedness, relationship to the study product or procedures, and severity. The CCTRN Study Sponsor will rely on the NHLBI DSMB to identify conditions or events that would trigger further action, including a temporary halt, modification, or termination of the study for safety reasons.

7.7 Review of Open Label Lead-in (six subjects)

The following outlines the process for the collection and review of data for the six subjects participating in the open label lead-in portion of the study:

1. Six subjects who consent and meet all inclusion and exclusion criteria will receive allo-MSC cell therapy per protocol.
2. All subjects will be observed for any complications or adverse effects of electromechanical mapping or delivery of cell therapy.
3. Events will be reported to regulatory oversight groups as outlined above in section 7.4.
4. The DSMB will review 1 month safety and feasibility data from each of the six subjects. These data will also be forwarded to the FDA in a subsequent amendment.
5. Upon successful DSMB review of the lead-in data, the study will be permitted to recruit the remaining approximately thirty subjects into both the active and placebo groups to the specified protocol sample size.

8.0 STATISTICAL PROCEDURES

8.1 Randomization Strategy and Monitoring

Randomization, or the random allocation of therapy, is a well-accepted mechanism for reducing potential bias in evaluating treatment effects. Randomization process, timing, and notification details are provided in section 4.6 above. Subjects will be randomized either to allo-MSCs or to placebo stratifying by center and using block sizes of 2.

The DCC will monitor recruitment by providing reports to the NHLBI Project Office as appropriate during the recruitment phase. Updated reports will be maintained on an Internet site accessible to Network members. Goals for recruitment will be set and will be reviewed by the DCC and the NHLBI Project Office.

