3.2 Study Design

This study will evaluate approximately thirty-six subjects. The first six subjects will receive allo-MSC therapy (open label) and will be assessed for safety and feasibility of the study procedures. Following 1 month data review of each of the six subjects by the NHLBI Gene and Cell Therapy Data and Safety Monitoring Board; this will be followed by a randomized, double-blind clinical trial enrolling approximately thirty subjects (see Section 7.7). These subjects will be randomized 1:1 to receive allo-MSCs or placebo. All subjects will undergo cardiac catheterization and study product administration using the NOGA Myostar catheter injection system. Subjects will be followed at 1 day, 1 week, 1 month, 6 months, and 12 months post study product injection. All endpoints will be assessed at the 6 and 12 month visits which will occur 180 ± 30 days and 365 ± 30 days, respectively, after the day of study product injection (Day 0).

For the purpose of the safety evaluations and endpoint analysis, we will utilize an “intention-to-treat” study population. In addition, because this phase I study is the first cell therapy study in this population, at 12 months all available standard-of-care medical records for cancer surveillance will be reviewed for cancer recurrence. Approximately thirty-six subjects will be enrolled over a 12-18 month accrual period.

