4.6 Randomization Procedures and Timing

Randomization to treatment assignment (cells or placebo) will be conducted using a web access database created and maintained by the Data Coordinating Center (DCC). The research coordinator (RC) will randomize the subject via the CCTRN web-based database which will perform the computer-generated randomization assignment and send automatic emails notifying the study team that the treatment assignment can be accessed by unblinded study team members with appropriate security credentials. The RC will not randomize the subject until the following criteria are met: i) the subject has provided written informed consent, ii) baseline evaluations are complete, iii) the inclusion and exclusion criteria for the study have been satisfied, and iv) MSC product is available at the cell manufacturing facility (CMF) should the subject be randomized to the cell group. Randomization should occur no less than 3 days prior to the scheduled SPI procedure (to allow time for cell shipping and local product preparation) and no more than 7 days prior to the scheduled SPI procedure (to minimize the risk of randomizing subjects who do not receive treatment).

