5.3 Blinding of the Interventionalist and Study Team

With regard to safety, the interventionalist must be able to visualize the study product to inspect that it looks safe (e.g., free of air bubbles, clumping, etc.). As the study product cannot be effectively masked, the process of blinding resides with endpoint and adverse event determination. The cMRI endpoint will be determined by core laboratories. Core laboratory evaluation of endpoint measures will be conducted by personnel who are blinded to therapy assignment. Coordinators and other personnel participating in the collection of cMRI, 6MWT, and the MLHFQ endpoint data will also be blinded to the therapy assignment. In addition, each of the clinical centers will take steps to ensure that adverse event assessments are carried out in a blinded fashion.

Local CPL and CCMF staff will be unblinded (see section 4.6) in order to assist with product preparation; however, the research teams (investigators, coordinators and other staff involved with endpoint data collection and event data) will be blinded to the treatment assignment. If for important medical reasons unblinding is thought to be necessary, the Investigator may identify the treatment assignment by contacting the DCC who is responsible for maintaining randomization records for all subjects.

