The MRI core lab provides the statement of any findings and also provides to the clinical team a weblink to the actual MRI images with instruction on the location of the finding(s) (i.e. which series/views will highlight it for their review). This allows the PI/interventionalist at the center to readily identify the location, view the images, and request additional info if needed. All studies

CONFIDENTIAL AND PROPRIETARY

are reviewed by the local radiologist for clinical findings for the PI's consideration before enrollment.

Identification and clinical evaluation of LV thrombus: The MRI core lab will provide their interpretation about the presence of a thrombus to the local center. The MRI core lab will differentiate between the LV thrombi that meet the definition of an exclusion on the one hand from the smaller LV thrombi that would likely not appear on echo. The MRI core lab will describe the latter by stating, "*cannot rule out small LV thrombus*". For these, it will then be up to the site study Principal Investigator and the interventionalist to follow up in making the determination of clinical significance of any finding and whether (and when) they would proceed with study procedures. This leaves the decision to proceed in the presence of the smaller LV thrombi identified by MRI in the hands of the site study PI based on their assessment of clinical significance. If they proceed, documentation of that determination must be included in the participant's chart.

6.6.3.1 Performance of MR examinations in subjects with implantable cardiac devices (ICD/pacemakers)

The presence of a pacemaker or implanted defibrillator device is not a contraindication to MRI scanning^{121,122}.

The procedures use are based upon the safety recommendations as listed in “Safety of Magnetic Resonance Imaging in Subjects With Cardiovascular Devices: An American Heart Association Scientific Statement”¹²¹. In particular, the recommendations include:

1. Written and verbal informed consent is obtained. Specific risks are documented, including
 - a. pacemaker/ICD dysfunction and/or damage
 - b. arrhythmia
 - c. device dislodgement
 - d. thermal injury
 - e. death
2. There is direct involvement of a cardiologist with pacemaker/ICD expertise, to oversee pre-scan device measurements, device changes including therapy (ICD) disabling for the duration of the scan, and post-scan measurements and re-enabling of therapy and other device parameters.

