8.2 Delays and Early Withdrawal from the Study

There may be circumstances in which randomized subjects experience a delay in receipt of study product. There may also be circumstances that do not allow for randomized subjects to receive study product. These circumstances are discussed further below. All randomized subjects who do not receive SPI in the expected timeframe will have their case reviewed by the Medical Monitor and SENECA Center PI to assess whether the subject should be withdrawn immediately or delay study procedures for another attempt.

Circumstances that may result in delaying SPI could be related to a change in the clinical condition of the subject or to an issue with local cell processing and product preparation.

1. A randomized subject who has a resolvable change in their clinical condition, and for whom the product has not yet been prepared for injection, will be allowed to have their SPI postponed.

2. If a cell processing related issue arises on the day of the SPI procedure and additional product can be delivered at a later time, the subject will have their SPI postponed.

Length of postponement will be determined by the Medical Monitor and SENECA Clinical Center PI upon review of the case details. The subject must remain eligible for the study in order to proceed with SPI, which may include repeat baseline testing. A subject who cannot be treated will no longer qualify for inclusion in the study, though will be included in all analyses for which they have data in accordance with the "intention-to-treat" principle.

In this first-in-human, phase I trial, SENECA's principal analysis will be "intention-to-treat". The anticipated small number of patients who are randomized but do not receive treatment will have the reason for non-treatment tabulated.

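### Fixed blocks of 2 within center, printed in the protocol, make the second assignment of each pair deducible, and the supplied text sets no disclosure or selection rule for the operator who sees the product

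*Combined protocol and SAP*

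**What the plan says.** - **Allocation.** Section 3.2 sets 1:1 allocation. Section 8.1 specifies randomization "stratifying by center and using block sizes of 2" and gives no other size. Section 9.3.1 requires each investigator to read the protocol, so the block size is known at the sites.
- **Masking.** Section 5.3 requires the interventionalist to inspect the product visually and continues: "As the study product cannot be effectively masked, the process of blinding resides with endpoint and adverse event determination". It adds that "the research teams (investigators, coordinators and other staff involved with endpoint data collection and event data) will be blinded to the treatment assignment". Section 5.4 refers to those who perform the catheter procedures as investigators, so the operator's own status under that sentence is unclear.
- **Timing.** Section 4.6: "Randomization should occur no less than 3 days prior to the scheduled SPI procedure", and no more than 7 days before it. The coordinator randomizes through a central web system once eligibility is complete. Section 3.2 has about 36 subjects "enrolled over a 12-18 month accrual period".
- **Operator input on entry.** For small left ventricular thrombi, section 6.6.3 leaves it to the site principal investigator and "the interventionalist to follow up in making the determination of clinical significance of any finding and whether (and when) they would proceed".

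**The concern.** In a 1:1 block of 2 the second assignment is always the opposite of the first. Someone who knows the first and the order of entry at that center knows the next arm before the next subject is chosen. The operator learns the first assignment by doing the procedure.

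The plan's safeguards address other matters. Central web randomization stops anyone reading the list, but it cannot hide an assignment that can be deduced. Blinded core laboratories and blinded event assessment protect measurement, not the choice of who enters or when. Section 5.3 says who should be blinded, but the supplied text does not say what the operator may disclose or whether the operator may help choose or order candidates.

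With about 15 subjects per arm, a few entries chosen with knowledge of the next arm could disturb baseline balance. In addition, one disclosed assignment unblinds two subjects.

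**Working it through.** The plan gives no figure for predictability, so there is none to reproduce.

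**Inputs from the documents:** 1:1 allocation (3.2); blocks of 2 within center (8.1); about 30 randomized (3.2, 7.7), up to 31 (3.3); injection 3-7 days after randomization (4.6); accrual over 12-18 months (3.2).

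**Assumption:** the number of centers, C, is not stated. I use 5 to 8, with 3 to 10 as a wider range.

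**1. Does the operator see the first product in time?** Treat the 12-18 months as the period for the 30 randomized subjects. With C = 5 a center enters 30/5 = 6; over 12 months that is one every 2 months. With C = 8 it enters 30/8 = 3.75; over 18 months that is one every 4.8 months. Against a 3-7 day wait for injection, the first product of a pair is usually seen before the second subject is randomized.

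**2. Certain assignments, blocks of 2.** A center with n subjects has floor(n/2) certain assignments, so the total is (30 - number of centers with an odd count)/2.

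- Subjects allocated to centers at random: on average about C/2 centers have an odd count, so the total is about (30 - C/2)/2. C = 5: 27.5/2 = 13.75, or 45.8%. C = 8: 26/2 = 13.0, or 43.3%.
- Counts as equal as possible: C = 5 gives 15, C = 6 gives 12, C = 7 gives 14, C = 8 gives 14. The range is 12-15 of 30.
- C from 3 to 10, any pattern of odd counts: 10-15 of 30.

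These are ceilings: they need every earlier assignment at the center to be known.

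**3. Correct guesses, blocks of 2.** All certain assignments are guessed correctly, and half of the rest. C = 5: 45.8 + 54.2/2 = 72.9%. C = 8: 43.3 + 56.7/2 = 71.7%.

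**4. Undisclosed random mix of blocks of 2 and 4.** For the first two subjects at a center, knowing the first predicts the second with probability 0.5 x 1 + 0.5 x (2/3) = 0.83 instead of 1. For the whole trial I simulated 30 subjects allocated at random to C centers. The guesser knows the set of block sizes and all earlier assignments at the center, but not the block boundaries.

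| | Blocks of 2 | Mixed 2 and 4 |
|---|---|---|
| Certain, C = 5 to 8 | 46% to 43% | 9% to 7% |
| Guessed correctly | 73% to 72% | 70% to 68% |
| Mean difference in arm size (patients) | 1.1 to 1.4 | 1.4 to 1.8 |

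Guessing the arm that is behind at the center needs no knowledge of block size, and it is right just as often in both columns. Withholding the sizes therefore removes certainty but not the informed guess.

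**5. Cost in precision if the arms end unequal.** SE ratio against 15 v 15 = sqrt[(1/a + 1/b)/(2/15)]. For 18 v 12 it is 1.021; for 17 v 13 it is 1.009.

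**The case against.** The route from knowledge to selection is thin. The coordinator randomizes, and only after consent, baseline testing and eligibility are complete. Main entry criteria lie outside the operator's hands: ejection fraction by cMRI, and recurrence risk as judged by an oncologist. The one documented operator input concerns small thrombi, is shared with the site principal investigator, and must be recorded in the chart. A center entering a subject every few months may have no queue to reorder, and section 4.5 allows at most 45 days from consent to injection. Very small blocks also have a sound purpose when centers enter about 4-6 subjects each. All of this stands. It limits the likely harm, but it does not conceal the second assignment.

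The supplied text is also incomplete. The Protocol Manual of Operations is not included. The contents list names a non-disclosure agreement whose page was removed; its title concerns materials and proceedings, but its text cannot be checked. The gap can be claimed only for the text supplied.

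Three stronger readings are tempting:

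- **That selection was in fact biased.** The documents do not show operators choosing or ordering candidates.
- **That the bias or the type I error can be quantified.** Any such figure would only return whatever amount of steering one assumes, and the documents supply none.
- **That section 8.2 discloses the arm to the site principal investigator.** It covers the case "If a cell processing related issue arises on the day of the SPI procedure and additional product can be delivered at a later time" and says: "Length of postponement will be determined by the Medical Monitor and SENECA Clinical Center PI upon review of the case details". That may hint at the cell arm, since placebo is cell-free and kept on site. But placebo also undergoes release tests before injection (5.2, Table 2b), and if the postponed subject is second in the pair, the other is already randomized. It is a possible hint, not a certain disclosure.

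**Conclusion.** The concern holds as a weakness in allocation concealment. The stated scheme makes the second assignment of each pair certain to anyone who knows the first; the operator sees an unmasked product; and the supplied text gives no rule on operator disclosure or on the operator's part in choosing candidates.

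Size, if all earlier assignments at a center are known: 43-46% of assignments certain on average and 72-73% guessable, for 30 subjects allocated at random to an assumed 5-8 centers. The certain count is 12-15 of 30 with equal counts at 5-8 centers, and 10-15 over 3-10 centers. An operator who performs only some of a center's cases knows less.

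The trial is not invalidated. Its primary purpose is safety and feasibility (1.1), cMRI is read by blinded core laboratories, and section 8.6 already calls the findings preliminary. This is a cheap improvement.

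**What to change.** 1. Keep stratification by center. For blocks not yet used, have the data coordinating center generate randomly varied blocks of 2 and 4. Remove the sizes from section 8.1 and hold them in a document restricted to that center. Sites have already read the current size, so withholding helps only together with new blocks.
2. State in section 5.3 that the injecting operator does not disclose what was seen and takes no part in choosing or ordering candidates at that center, apart from safety and procedural-suitability input such as sections 4.3 (item 7), 5.5 and 6.6.3 call for. Clarify there whether the investigators listed as blinded include the operator. If a manual already contains such a rule, cite it.

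**Cost:** a new list and short amendments to 5.3 and 8.1. Mean arm imbalance rises by about 0.3-0.4 patient; even an 18 v 12 split widens the standard error by only 2.1%. The gain is large for certainty (43-46% down to 7-9%) but modest for guessing (72-73% down to 68-70%), and the block change helps only where blocks remain unused. The operator rule therefore matters at least as much as the new blocks.

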8.2 Delays and Early Withdrawal from the Study

There may be circumstances in which randomized subjects experience a delay in receipt of study product. There may also be circumstances that do not allow for randomized subjects to receive study product. These circumstances are discussed further below. All randomized subjects who do not receive SPI in the expected timeframe will have their case reviewed by the Medical Monitor and SENECA Center PI to assess whether the subject should be withdrawn immediately or delay study procedures for another attempt.

Circumstances that may result in delaying SPI could be related to a change in the clinical condition of the subject or to an issue with local cell processing and product preparation.

1. A randomized subject who has a resolvable change in their clinical condition, and for whom the product has not yet been prepared for injection, will be allowed to have their SPI postponed.

2. If a cell processing related issue arises on the day of the SPI procedure and additional product can be delivered at a later time, the subject will have their SPI postponed.

Length of postponement will be determined by the Medical Monitor and SENECA Clinical Center PI upon review of the case details. The subject must remain eligible for the study in order to proceed with SPI, which may include repeat baseline testing. A subject who cannot be treated will no longer qualify for inclusion in the study, though will be included in all analyses for which they have data in accordance with the "intention-to-treat" principle.

In this first-in-human, phase I trial, SENECA's principal analysis will be "intention-to-treat". The anticipated small number of patients who are randomized but do not receive treatment will have the reason for non-treatment tabulated.

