5.2 Placebo Group

Subjects randomized to the placebo group will undergo the same baseline testing and imaging as those in the allo-MSC group. The placebo will be kept on site at the local CPLs. The fifteen

CONFIDENTIAL AND PROPRIETARY

patients in the placebo group will receive transendocardial injections of cell-free Buminate solution in 20 injection sites. The placebo product will undergo QC testing before injection as indicated in Table 2b.

Table 2b. Testing of Placebo for Injection

Assay	Test Method	Specification
Rapid Sterility*	Gram Stain	No organisms
Endotoxin*	EndoSafe PTS	< 5EU/kg**
Aerobic, Anaerobic, and Fungal	14 day Bactec/BacT/ALERT assay or equivalent	No Growth

* Tests done for release criteria specification prior to injection

** Based on recipient weight and product volume

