6.5 Follow-up Tests Performed After SPI

Randomized subjects will be followed up at 1 week and 1, 6, and 12 months after study product injection for regular history and clinical examination. The MLHFQ will be repeated at 6 and 12 months after SPI. To further evaluate their functional capacity, subjects will also undergo a 6MWT at 6 and 12 months after SPI. Subjects will be assigned a functional class during the month 1, 6, and 12-month follow-up visits based on the standard NYHA classification. Patients treated with allo-MSCs or placebo will undergo the following tests at various time points after the procedure (Table 3):

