6.5.7 Follow-up Windows

The timeline for follow up will initiate with the day of SPI (Day 0). The time windows for each of the subsequent follow up visits will be as follows:

1. The 1-week visit will be 7 ± 3 days (from day of SPI).
2. The 1-month visit will be at 30 ± 7 days.
3. The 6-month visit will be at 180 ± 30 days.
4. The 12-month visit will be at 365 ± 30 days.
5. The 24-month phone call will be at 730 ± 30 days.

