6.5.8 Lost to Follow-up

Randomized subjects will be followed for up to two years. Subjects will be considered lost to follow-up after 3 consecutive failed telephone contacts AND one certified letter returned to the site. Contact attempts will be documented in the subject's study chart.

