9.1.2.2 Cell Processing

For those patients receiving the allo-MSC cell product, it is possible that the body might react and reject the allo-MSC cells. Human clinical research studies with allo-MSCs in heart patients have provided evidence against the occurrence of rejection of the transplanted cells and also against the occurrence of GVHD, where healthy infused cells recognize the tissues of the person receiving the cells as "foreign" and mount an immunologic attack.

Processing the cells is done under strict sterile conditions; however, there is a rare chance that the cells could get contaminated while being processed. Testing will be done on the cells; however, it takes about 2 weeks to get the final results. If the tests show cells were contaminated, the treatment team will be notified so that the patient may be treated with antibiotics. Subjects will be taking their temperature twice a day for one week, which may help determine infection before the test results are known.

There may be some circumstances where the patient is unable to receive the processed cells; such as a processing failure or poor quality of the cells. If events such as these occur, the patient will not receive the allo-MSC cells but will be asked to continue with follow up in the study. Processes in place to prevent these failures include: the use of standard operating procedures for preparing the allo-MSC cell product, which will identify any problems with the study product before it is released, and continuous temperature monitoring of the product during shipment to the treatment facility.

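### Sections 8.2 and 9.1.2.2 disagree on whether a randomised subject who cannot be injected stays in follow-up, and neither gives that subject a visit schedule, so the intention-to-treat analysis may lack 6- and 12-month outcomes

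*Combined protocol and SAP*

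**What the plan says.** Sections 3.2 and 8.2 make intention-to-treat the basis of the safety and endpoint analyses. The plan then treats a randomised but uninjected subject in three ways.

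- **Section 8.2.** Any randomised subject not injected on time has the case reviewed by the Medical Monitor and the centre investigator to "assess whether the subject should be withdrawn immediately or delay study procedures for another attempt". If treatment proves impossible: "A subject who cannot be treated will no longer qualify for inclusion in the study". The same sentence goes on, "though will be included in all analyses for which they have data", citing the intention-to-treat principle. Reasons for non-treatment are to be tabulated.
- **Section 9.1.2.2.** Where cells cannot be given because processing fails or their quality is poor, "the patient will not receive the allo-MSC cells but will be asked to continue with follow up in the study".
- **Sections 6.5 and 6.5.7.** "Randomized subjects will be followed up at 1 week and 1, 6, and 12 months after study product injection". Section 6.5.7 makes the day of injection Day 0 for every visit window and for the 24-month call. Section 6.5.8 adds "Randomized subjects will be followed for up to two years" but names no starting date.

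Section 7.3 starts event reporting at consent and ends it 30 days after the 12-month clinic visit.

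**The concern.** Suppose a subject is randomised to cells, the product fails release on the day, and no replacement can be had. Section 8.2 ends that subject's participation; section 9.1.2.2 asks for continued follow-up. A site cannot do both. If it follows 9.1.2.2, it still has no Day 0 from which to date the 6- and 12-month visits, and section 7.3 ties the end of event reporting to a 12-month visit that has no date.

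If the site follows 8.2, collection stops. The subject stays in the analysis set in name but has no late outcomes. Section 8.3.2.1 specifies Fisher's exact tests from baseline to 6 and to 12 months without saying who is in the denominator when follow-up ends early. The Wilcoxon comparisons in section 8.3.2.3 need a change score that this subject will not have. In the mixed model the subject can contribute a baseline value and nothing about change.

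Two feasibility measures in section 3.4.2 would also overlap: a subject precluded from injection would count as failing to complete follow-up because the protocol ended it.

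**Working it through.** **Step 1. The plan's own figure.** The only related number is the loss allowance in section 3.5.

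- 0.15 × 30 = 4.5, as stated; with the 31 named in the same paragraph, 0.15 × 31 = 4.65.
- 30/(1 − 0.15) = 35.3, rounded up to 36. 31/(1 − 0.15) = 36.5, rounded up to 37. These match 30 + 6 and 31 + 6.

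The arithmetic is not in dispute. However, section 3.5 presents the six as cover for losses, while section 3.3 uses six as the open-label lead-in. The randomised cohort may therefore hold no reserve for untreated subjects.

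**Step 2. Listed causes, by arm.**

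- Section 5.5: seven events before or during injection, all possible in either arm.
- Section 8.2: two causes of delay. One is a clinical change (either arm); the other is a processing or preparation problem.
- Section 9.1.2.2: two examples, both specific to cells.

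Of 7 + 2 + 2 = 11 items, 2 are strictly cell-only, or 3 if the processing item in 8.2 is counted; 8 can occur in either arm. The handling still differs. Cells are shipped frozen, thawed, washed and released on viability and cell count as well as Gram stain and endotoxin (sections 5.1.1 and 5.1.2, Table 2a). For the comparator, "The placebo will be kept on site at the local CPLs", and release rests on Gram stain and endotoxin alone (Table 2b). The cell arm therefore carries extra ways to fail on top of the shared ones.

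**Step 3. Size.** Inputs: 15 per arm (Executive Summary). The documents give no non-treatment rate, so the number lost, k, is an assumption. Take k lost from one arm and none from the other.

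- Share of the arm missing = k/15.
- Standard error of the difference, relative to no loss = √{[1/(15 − k) + 1/15] / (2/15)}.
- Shift in that arm's mean = (k/15) × d, where d is the difference, in SD, between lost and retained subjects; shown for d = 1.

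| k | Missing | SE ratio | Shift for d = 1 |
|---|---|---|---|
| 0 | 0% | 1.000 | 0 |
| 1 | 6.7% | 1.018 | 0.07 SD |
| 2 | 13.3% | 1.038 | 0.13 SD |
| 3 | 20.0% | 1.061 | 0.20 SD |

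The chance of at least one untreated subject among 15 is 1 − (1 − p)^15. For assumed p of 2%, 5% and 10% it is 0.26, 0.54 and 0.79.

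**Step 4. Events.** Assume three subjects with MACE in an arm of 15, 3/15 = 20%. If one of them was withdrawn uninjected and the event came later, the arm shows 2/14 = 14.3% if the subject is dropped, or 2/15 = 13.3% if counted as event-free. The plan does not say which.

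**Step 5. Choice of visit origin.** Section 4.6 places randomisation 3 to 7 days before the scheduled injection. Dating visits from randomisation or from the scheduled injection thus differs by at most 7 days if the date is not moved, against windows of ±30 days at 6 and 12 months.

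**The case against.** The strongest reply is that the plan already contains most of what is needed. Section 8.2 does not exclude anyone from analysis: the clause after the sentence quoted keeps these subjects in wherever data exist. Event reporting starts at consent, so events before a withdrawal are captured. Section 4.6 requires product to be available before randomisation and keeps the gap to injection short, expressly to limit untreated subjects. Reasons for non-treatment and failures to complete follow-up are both reported, so the loss would be visible. Section 8.6 already calls the findings preliminary.

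Much of this stands, and it rules out several stronger readings that a reader might infer:

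- **That 8.2 removes subjects from the analysis.** It does not; it ends participation. The problem is missing late data, not exclusion by treatment received.
- **That most causes of non-treatment are confined to the cell arm, so follow-up is lost from one arm.** Step 2 shows otherwise. Placebo can fail release testing too. The strictly cell-only causes are those section 9.1.2.2 keeps in follow-up, and the processing item in 8.2 leads to postponement when more product can be delivered.
- **That baseline is reset in one arm.** Section 8.2 mentions repeat testing in connection with continued eligibility. It does not say that repeat values replace the originals, and it covers clinical postponements in either arm.
- **That deaths or heart-failure events are hidden.** Only events after an actual withdrawal could be missed.

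What the reply does not answer is the contradiction, the absent visit origin, and the fact that keeping available data cannot recover outcomes nobody collected. The safeguard in 4.6 concerns product at the manufacturing facility; it does not cover failure in shipment, thawing or local release.

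**Conclusion.** The plan is wrong as written on this point and should be changed. Sections 8.2 and 9.1.2.2 give conflicting instructions for a subject with a cell-processing failure, and sections 6.5 and 6.5.7 leave any uninjected subject without a 6- or 12-month visit. The promised intention-to-treat analysis may therefore lack late safety and endpoint data on randomised but untreated subjects, and the loss may be unequal between arms.

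The size cannot be computed from the documents, which give no rate and anticipate few such subjects. Each is 6.7% of a 15-subject arm. Under the assumed range of one to three losses from one arm, the cost in precision is small (standard error up 1.8% to 6.1%). The possible shift is 0.07 to 0.20 SD for each SD by which lost and retained subjects differ. In a first-in-human safety comparison this small, one missed event changes the observed rate noticeably.

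**What to change.** 1. Reconcile section 8.2 with section 9.1.2.2: every randomised subject, injected or not, is asked to stay in follow-up for events and for the 6- and 12-month measures unless consent is withdrawn. Whether to attempt or postpone injection remains a separate decision, untouched by this change.
2. In section 6.5.7, set one visit origin for uninjected subjects in both arms, for example the scheduled injection date or the randomisation date. The end of event reporting in section 7.3 then has a date as well.

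The cost is protocol wording, with consent wording to match, and a few ordinary follow-up visits. Those include cMRI with contrast at 6 and 12 months in people who were not treated; section 9.1.2.4 describes the contrast risks, so this burden is real though limited to few subjects. Keeping untreated subjects in also dilutes the estimated effect among those treated somewhat; a secondary as-injected table can show that.
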